4.4 Short Physical Performance Battery (SPPB)

Every six weeks (regularly scheduled clinic visits) patients will undergo the short physical performance battery [APPENDIX E]. This will result in a total of four SPPB measurements. This test will be administered by the Clinical Research Coordinator (CRC) in-person or the physical therapist virtually and scores will be captured. The SPPB¹⁹ is a validated tool used to assess lower extremity functioning. It is comprised of three objective measures testing for standing balance, normal gait speed, and strength performance by use of a timed sit-to-stand. The participants are asked to stand with their feet side by side, semi tandem, and tandem for 10 seconds each to assess balance. Normal gait speed is tested by asking participants to walk 8 feet at his or her normal speed. Strength performance is tested by asking participants to complete five timed chair sit to stands without the use of hands. These three measures are scored individually from 0 to 4 with an aggregate score ranging from 0 to 12, with higher scores correlating with a

greater functional status. The scores are then classified into 4 categories; very low physical function (0-3); low physical function (4-6); moderate physical function (7-9); and high physical function (10-12). This tool can be administered in under 10 minutes and has been found to accurately predict falls, disability, and nursing home admissions among older adults.¹⁹ It also has been found to be a prognostic biomarker among older adult cancer survivors²⁰ as well as serve as Quality of Life predictors.²¹ In order to support safety at home for patient while performing test, physical therapist will instruct patient to perform test near stable surface that patient can support themselves on in order to reduce fall risk. If at any point during test patient demonstrates fall risk physical therapist will hold from advancing on to the next phase of the test.

4.5 6 Minute Walk Test

If patients are able to see PT in-person the 2 or 6 minute walk [APPENDIX F] test will be done as an additional physical function measure. This will be performed every 6 weeks. [APPENDIX F]. The 6MWT (6 Minute Walk test) is a validated tool used to assess endurance and overall functional exercise capacity.²² Patients are instructed to walk on a treadmill at their own pace for as long as they are able. At the end of the allotted 6 minutes patients are told to stop and the total distance covered is recorded. Participants walking less than 300 meters are considered to have low endurance while those walking over 300 meters are considered to have normal endurance.²³ The distance covered has been found to be strongly related to important clinical outcomes and is positively associated with peak exercise capacity and quality of life, and negatively associated with risk of disease exacerbation, number of hospitalizations, and mortality.²⁴ If the patient is unable to perform the 6-minute walk test, they will be transitioned to the 2-minute walk test.

4.6 Functional Status Assessments

The Functional Status Assessment survey [APPENDIX G] will be assessed every 3 weeks by the CRC either in person, by phone, by email, or through virtual health monitoring. These surveys will be comprised of 16 activities including seven Activities of Daily Living (ADL) measures⁷, 5 Instrumental Activities of Daily Living (IADL) measures²⁵, and 3 mobility activities.⁹ For each activity, disability is defined as the need for personal assistance or inability to perform the activity. Activities are scored as 0 being no help, 1 being with help, and 2 meaning unable to perform the activity. Higher scores indicate greater disability or a lower functional status. The ADL trajectories will include; eating, grooming, bathing, dressing, walking, toileting, and transferring, the IADL trajectories include; shopping, housework, meal preparation, taking medications, and managing finances, and the mobility measures will include; walking a quarter mile, climbing a flight of stairs, or lifting/carrying a 10lbs. The final mobility activity included is if the participant drove a car in the past month, where disability is defined as having not driven. In addition to these 16 measures, the patients will undergo the EQ-5D-5L [APPENDIX H]. The EQ-5D-5L²⁶ is a brief 5 question assessment that captures disability in self-care, mobility, and usual activities. It uses a scoring scale from 3, meaning no disability to 15 points, indicating severe disability. This tool has been mapped to the EORTC-QLQ-C30,²⁷ specifically in patients with advanced NSCLC²⁸. However, the EQ-5D-5L has been shown to be the preferred assessment due to its shortened length and its improved sensitivity and face validity.²⁶

4.7 PROMIS-10

The Patient-Reported Outcome Measurement Information System (PROMIS) Global Health Scale Short Form v1.1 HRQL [APPENDIX I] is the most widely used self-rated health item. It has been shown to be a useful tool in screening for disability and improving communication between patients and clinicians.²⁹ This assessment consists of each domain of health with items representing physical health, pain, fatigue, mental health, social health, and overall health. Each of the 10 measures consist of five responses; Excellent, Very good, Good, Fair, and Poor. The CRC will administer the PROMIS by use of iPads during the patient's regularly scheduled visits or by phone approximately every 6 weeks.

4.8 GAD-7

The GAD-7³⁰ [APPENDIX J] is a reliable tool used to assess the prevalence and severity of Generalized Anxiety Disorder (GAD) in clinical settings. This assessment is a 7 item questionnaire that asks patients how often in the past 2 weeks, have they been bothered by each symptom. The responses are scored as 0 being "not at all," 1 being "several days," 2 being "more than half the days", and 3 being "nearly every day," for an aggregate score of 21. Higher scores indicate a higher prevalence of anxiety and are strongly associated with multiple domains of functional impairment and disability days.³⁰

4.9 PHQ-9

The Patient Health Questionnaire is a self-administered assessment used for diagnostic purposes of common mental disorders.³¹ The PHQ-9 [APPENDIX K] is the 9-item depression segment which assesses the severity of depressive symptoms within the last two weeks. Patients will complete the PHQ-9 approximately every 6 weeks administered by the CRC. Items are scored from 0-3 with higher scores indicating greater levels of depression. If 5 or more of the 9 symptoms have been present for "more than half the days," then major depression is indicated. Other depression is indicated if 2, 3, or 4 of the symptoms have been present at least "more than half the days" in the past 2 weeks, and 1 of the symptoms is depressed mood or anhedonia.

4.10 EORTC QLQ-C30 and EORTC QLQ-LC13

The EORTC QLQ-C30 [APPENDIX P] is a widely used quality of life assessment for cancer patients.³² It is comprised of five functional scales, three symptom scales, a global health scale and one quality of life scale. This measure takes an average of 11 minutes to complete and is a reliable and valid measure to assess quality of life in cancer patients. The EORTC QLQ-LC13 [APPENDIX Q] is a modular supplement to the EORTC QLQ C30. This is a 13 item lung cancer-specific questionnaire that assesses for symptoms such as coughing and dyspnea.³³ It has been shown to be a valid assessment for monitoring symptoms in patients with a thoracic malignancy. Patients will complete both the EORTC QLQ C30 and the LC13 along with the other assessments during their regularly scheduled visits.

4.11 POMS-Revised

The original POMS is 65 items. The POMS Short Form (POMS-SF) is 37 items and there are many studies that have shown its reliability and validity. The “POMS-12” {APPENDIX R] was created in the following way.³⁴ Factor analysis of the 37-item version identified 6 factors, which are identified as the subscales. For each subscale, the two items with the largest factor loading were selected and included in this abbreviated version. This method has been validated in previous research.

4.12 Biomarkers

Peripheral blood and stool samples will be collected at baseline prior to treatment and pre and post PT + PMR session. Thereafter, blood will be collected every 6 weeks pre and post PT + PMR session and at additional triggered time points for correlative biomarker studies. Each patient will have a minimum of 6 research blood draws performed (2 pre-treatment) and 4 total post-treatment. The post-PT +PMR blood sample will be drawn from the peripheral IV so an additional needle stick is not required. The blood will be processed into peripheral blood T lymphocytes (PBTLs), plasma, and serum for cellular senescence correlative analyses. The analysis consists of routine laboratory values including hematologic functions, renal function, hepatic function and calculated creatinine clearance, and markers of inflammation and coagulation, and potential molecular markers of aging (P16^{INK4a} Expression, DNAge). The details of this biological assessment are below:

Table 2: Biomarker Assessment

Laboratory Values captured in Routine Practice	Biologic Correlates*
Hematologic functions: WBC HGB Platelets Absolute Neutrophil count Absolute Lymphocyte count Absolute Lymphocyte count	Molecular markers of aging: OSU_Senescence DNAge Inflammatory Cytokines Peripheral blood T Lymphocyte subtyping
Renal Function: BUN Creatinine	
Hepatic function: AST ALT Total Bilirubin Alkaline Phosphatase Albumin	

*patients who have already begun treatment prior to visit 1 will not partake in research blood samples in order to preserve the integrity of the data.

Stool samples will be used for microbiome correlative analyses. At their clinic visit patients will be given a home microbiome collection kit that includes instructions for collecting a sample within 24 hours of their next clinic visit. (Please see **APPENDIX L** for the instructions included in this box.) Briefly, a rigid plastic scaffold is placed over the toilet seat to collect stool in a plastic tub. Patients return the sample at their next clinic. Staff transfer the samples to the [name] lab (IBC 2018R00000115) where stool is transferred to cryo-vials and stored at -80C until processing in batch.

DNA is purified using the QIAGEN PowerSoil kit and the 16S rDNA amplified using barcoded universal primers (V3-V4). Sequencing is performed on an Illumina MiSeq 2x300 for 16S to a depth of > 105k reads per sample. Demultiplexed fastq files are cleaned and paired using [name] Lab resources in the Ohio Supercomputing Center and analyzed following the DADA2³⁵³² pipeline in R³³.

Sequences are processed to identify amplicon sequence variants (ASVs) and then to closest taxonomic identification using the SILVA³⁴ and GreenGenes³⁵ databases. Metabolic pathway composition is inferred using the PICrUST pipeline. Samples are clustered by ASV abundances using Non-Metric Multidimensional Scaling³⁶, with the significance of clusters defined by the multi-response permutation procedure³⁷, calculated in the vegan package in R³⁸. The alpha diversity metric Simpson's Index calculated to quantify the number of species and evenness of the stool microbiome samples. Taxon abundances, at each taxonomic rank, and pathway abundances are modeled using formulae appropriate for each hypothesis, most commonly using the DESEQ2 package in R to accommodate the negative binomial distribution of microbial abundances³⁹.

4.13 Toxicities

The toxicity assessment and chemo drug & dose information will be collected by the CRC or a member of the clinical team at the beginning of every treatment cycle. Therapeutic toxicity will be collected using NIA Common Toxicity Criteria for Adverse Event v5 (CTCAE v5)⁴⁰. During each scheduled doctor's appointment or telephone encounter a research staff member or nurse will collect the therapy toxicities including grade and attribution to therapy. Additional toxicities may be collected from clinical encounters (scheduled or emergency visits) within the medical record. The clinical encounters include clinic notes, emergency room visits, and hospitalization. Furthermore, dose reductions, dose delays or discontinuation of the therapy course and the cause of each aforementioned event will be recorded.

Serious Adverse Event (SAE) per the NIA Common Toxicity Criteria for Adverse Event v5 (CTCAE v5)⁴⁰ is defined as any adverse event that results in one of the following: 1.) death; 2.) a life-threatening event; 3.) inpatient hospitalization or prolongation of an existing hospitalization >24 hours; 4.) persistent or significant incapacitation or substantial disruption to the participants ability to conduct normal life functions; 5.) congenital anomaly/birth defect; 6.) Important Medical Events (IME) that may not result in death, be life threatening, or require hospitalization but may be considered serious when, based upon medical judgement, the event may jeopardize the patient

and may require medical or surgical intervention to prevent one of the outcomes listed in the definition. The occurrence and incidence of SAE will be documented as part of toxicity assessment per CTCAE guidelines at each treatment visit.

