Patients enrolled in this study will complete baseline assessments consisting of demographic information, disease assessment, functional status assessments, depression/anxiety screenings, a quality of life measure, toxicity assessment, as well as a physical performance and an endurance test. A study coordinator will assess functional status every 3 weeks either in person, by phone, or virtual health monitoring. Participants’ clinical outcomes will be collected every 6 weeks during their regularly scheduled clinic visits (baseline, 6 weeks, 12 weeks, and 24 week time points). Triggered assessments will be collected on patients with any presence of disease progression, a new toxicity grade, fall, or healthcare utilization such as emergency department visit, inpatient admission, or worsening functional status on either survey. The study intervention will last approximately 12 weeks (3 months). If a patient cancels due to scheduling conflicts or treatment fatigue they will be given the option to reschedule their visit. At the end of the 12 weeks if a patient is still benefiting from PT then those missed visits can be scheduled out. Study assessments will still take place at 12 weeks in an effort to control for time-varying confounders. In the case a patient does make up any visits beyond the study 12 week time period there will be an additional study visit that takes place. This will be an “end of treatment” visit rather than a 12 week visit. The same study assessments performed at baseline will be completed at this time. The patients will be followed until 24 months post-enrollment for 1-year and 2-year overall survival. An additional qualitative assessment will be conducted on those patients that are agreeable and consent to being either video or voice recorded. Patients will participate in a semi-structured interview to assess overall study acceptability. This assessment will help capture the “joy” our novel supportive care intervention brings to the patient, patient’s family, and clinic team.

Figure 1. Study Schema

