An exercise log in the patient's electronic medical record will be filled out after each workout to keep track of patient progress. The patient will first be prescribed weekly sessions, then it will increase to twice weekly, then three times weekly based on patient behavior and activity tolerance. One session per week will be supervised virtually or in-person by the physical therapist. Additional sessions will be done by the patient on their own per standard-of care physical therapy practice. During the virtual health sessions, the physical therapist will assess barriers to doing their physical therapy and will problem solve with the patients on how to improve adherence. Please see [Appendix B] for a detailed description of the study exercise log.

Physical Therapy Safety Procedures

Upon the initial in-person visit the physician team or physical therapist will perform a standard-of-care safety screening of pulse oximetry assessment, heart rate and blood pressure monitoring, asking if patient has cardiac or pulmonary history. This screening will take into account if the patient is on oxygen, wears glasses or hearing aids. The in-person visit will also determine the location of the VH physical therapy, their emergency contact, and will verify their home address. It will be recommended that the patient perform their physical therapy in the same location each time. The physical therapist will perform a VH safety checklist at the beginning of each session. This checklist may include but not limited to the following questions:

- Where are you currently located?
- Is anyone else home with you?
- Is your cell phone charged and located near you?
- Have you had any new or different chest pain in the last week?
- Have you had any new or different shortness of breath in the last week?

During the VH visits, similar to an in-person visit, if the patient experiences any sudden chest pain or shortness of breath, they will be instructed to stop the activity, sit-down, and call their emergency contact within the home. If they are unable to call for help or are home alone, the physical therapist will call 911 and will notify the treating physician.

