4.18 Potential Risks

[figure not shown]
Our study team anticipates that there will be minimal physical and psychological risks or discomforts for the study participants. Informed consent will be obtained from all participants prior to study enrollment to ensure all potential risks are understood by participant. There is a small risk that patients have some distress associated with the completion of the study questionnaires. However, if this occurs, questions are easily skipped and the study staff will speak to the participant about the distress that the surveys have caused and will offer referral to a mental health professional if necessary. There is also a small risk of injury due to the prescribed exercise intervention. Patients will be taught by a licensed Physical Therapist how to safely

perform these exercises and instructed to only perform each task to the level of his or her physical ability. A safety checklist will be performed as detailed above before every physical therapy session. In the case of an injury, the on-study Physical Therapists will assess the patient and his or her exercise intervention may be modified accordingly.

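### Adverse events are attributed only to anticancer therapy: the plan states no relatedness to PT or PMR, and no route into the AE record for non-serious harms of the programme

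*Combined protocol and SAP*

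**What the plan says.** **Collection and attribution (4.13).** "The toxicity assessment and chemo drug & dose information will be collected by the CRC or a member of the clinical team" at the start of each treatment cycle. At appointments and telephone encounters, "a research staff member or nurse will collect the therapy toxicities including grade and attribution to therapy". The section also states that "dose reductions, dose delays or discontinuation of the therapy course and the cause of each aforementioned event will be recorded". On serious events: "The occurrence and incidence of SAE will be documented as part of toxicity assessment per CTCAE guidelines at each treatment visit". Further toxicities may be taken from clinic notes, emergency visits and hospital records.

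**The intervention's own risk (4.18).** Exercise injury is named as a small risk. If one occurs, "the on-study Physical Therapists will assess the patient and his or her exercise intervention may be modified accordingly".

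**Sessions (4.2).** One session a week is supervised, and frequency may rise to three a week. "Additional sessions will be done by the patient on their own per standard-of care physical therapy practice". A log is completed after each workout. Each virtual session opens with a safety checklist whose listed items are location, company, phone, and new chest pain or breathlessness in the past week; the list is expressly not exhaustive. For sudden symptoms during a session, the patient stops, sits and calls the contact at home. "If they are unable to call for help or are home alone, the physical therapist will call 911 and will notify the treating physician".

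**Triggers (4.1).** Study assessments are triggered by "disease progression, a new toxicity grade, fall, or healthcare utilization such as emergency department visit", and also by admission or worsening function.

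**Reporting (5.2.3).** Unexpected SAEs are reported within 48 hours and other SAEs within 72 hours. All AEs go to the principal investigator and research team. Expected AEs, with chemotherapy toxicity as the example, are filed in REDCap but not reported onward.

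**Analysis (6.1 to 6.2.1).** Feasibility is recruitment, adherence and retention. No harms summary is listed.

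**The concern.** A pilot of an exercise and relaxation programme should be able to say how often the programme hurt someone. Here the AE system is built around the background drug treatment. Followed as written, it would yield a graded record of chemotherapy and immunotherapy toxicity, with the causal question asked about the wrong treatment.

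Two things are at stake. First, in advanced lung cancer most events will have a plausible disease or drug explanation, so without a recorded judgement on PT and PMR the programme's contribution cannot be separated afterwards. Section 5.2.3 promises continuing review of risk against benefit, and that review needs this separation. Second, the harms most typical of such a programme (strains, minor injuries, distress during relaxation) are non-serious, so they fall outside the one reporting route that is independent of cause. This matters more because section 3.4 sets no exclusion for performance status, comorbidity or brain metastases.

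**Working it through.** The plan gives no figure on this point to reproduce. The check is a reading of the sections against each other, followed by an illustration.

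**1. What therapy means in 4.13.** It could in principle include physical therapy. The surrounding text rules that out: collection is tied to chemotherapy drug and dose and to treatment cycles, and the therapy course is one that can have dose reductions and delays. Attribution is therefore to anticancer treatment.

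**2. Where each kind of event goes.**

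| Event | Stated capture | Stated relatedness to PT or PMR |
|---|---|---|
| SAE, any cause | 4.13, reported under 5.2.3 | None |
| Chest pain, breathlessness | Weekly checklist, 4.2 | None |
| Fall, emergency visit, admission | Triggered assessment, 4.1, once staff learn of it | None |
| Non-serious exercise injury | Therapist assesses and may modify exercise, 4.18; no step into the AE record | None |
| Distress during PMR | None found | None |

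The last column is empty throughout. The capture gap is confined to the last two rows, and to falls that nobody reports, since no listed checklist item asks about falls.

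**3. Timing.** Section 4.13 documents SAEs at treatment visits, whereas section 3.1 places virtual sessions in non-treatment weeks. The study calendar (8.0) marks toxicities at baseline and weeks 4, 7, 10, 13 and 24, not under the treatment-visit column. These need reconciling. The weekly PT contact is not named as an AE collection point in either place.

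**4. Exposure.** Supervised sessions: 12 per patient. At three sessions a week throughout, which is an upper bound because the plan starts at one, the total is 3 × 12 = 36, of which 36 − 12 = 24 (67%) are unsupervised.

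**5. What full capture would buy.** With zero related events in n patients, the one-sided 95% upper bound is 1 − 0.05^(1/n).
- n = 20 (sections 1.1 and 3.1): 13.9%.
- n = 30 (enrolment figure in 6.1): 9.5%.

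**6. What incomplete capture costs.** Let p be the true share of patients harmed and c the share of those harms that are recorded as related. Both are assumptions; neither is in the plan. The chance of recording at least one is 1 − (1 − pc)^n.

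| n | p | c = 1 | c = 0.5 | c = 0.25 |
|---|---|---|---|---|
| 20 | 5% | 64% | 40% | 22% |
| 20 | 10% | 88% | 64% | 40% |
| 30 | 5% | 79% | 53% | 31% |
| 30 | 10% | 96% | 79% | 53% |

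With capture c, a zero count bounds pc and not p. At c = 0.5 the bound on p becomes 13.9/0.5 = 27.8% for 20 patients, or 9.5/0.5 = 19.0% for 30. When c is unknown, as it is here, no bound on p follows from the AE record.

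**The case against.** The strongest reply is that the plan has more safety machinery than section 4.13 suggests, and much of that reply stands.

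- A reader might infer that harms of the programme would go unreported. For serious events the documents do not support this. An SAE is defined without regard to cause, the 48- and 72-hour reporting rules carry no attribution condition, and captured AEs are reviewed by the principal investigator.
- A reader might infer that patients are not asked. That is also too broad. Chest pain and breathlessness are asked about weekly over a period that includes home sessions, the checklist is open-ended, and falls and emergency visits trigger assessments. A log follows every workout, so it would be wrong to say that unsupervised sessions pass with no record or later question.
- A reader might infer from the emergency procedure that chest pain handled by someone at home leaves no trace. Physician notification is indeed written for one branch only, but the workout log and the next checklist could both pick the event up.
- A reader might infer that the programme would be taken forward on follow-up alone. Section 6.1 also sets recruitment and adherence criteria, and 5.2.3 allows termination if significant risks emerge.
- The exercise log, PMR log and list of captured data points (Appendices B, D and O) were not available. A harms field there cannot be ruled out.
- All-cause counts of SAEs, falls and emergency visits would still bound related events of those types from above.

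What the reply does not supply is relatedness to PT or PMR, in any section. Investigator review covers only AEs that reach the record, and a fall trigger works only if someone hears of the fall. Because no expected PT or PMR events are listed, a foreseeable exercise injury could be classed as expected and filed without onward report.

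**Conclusion.** The point holds, within limits. As written, the plan attributes events to the background treatment and not to the intervention under study. It states no route into the AE record for non-serious intervention harms, and it plans no harms summary in section 6. It does not hold that serious events go unreported or that patients are never asked about symptoms.

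No sample size, error rate or decision threshold changes. The cost is in what the pilot can conclude: a bound of 13.9% (20 patients) or 9.5% (30 patients) after zero related events is available only with complete capture and attribution. The conclusion assumes that the unseen appendices do not already hold relatedness and injury fields; if they do, the remedy shrinks to cross-referencing them in 4.13 and adding the summary. The capture shares in the working are illustrative. This should be corrected as an inexpensive improvement to the safety information; it does not invalidate the design.

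**What to change.** 1. In 4.13, record for every AE and SAE a separate relatedness to PT and to PMR, alongside anticancer therapy.
2. Add to the weekly virtual-session checklist in 4.2 one fixed question on falls and injuries since the last session, naming home sessions explicitly.
3. State in 4.2 and 4.18 that injuries, stopped sessions and emergency calls seen by the physical therapist are entered in the study AE log. This concerns recording only and leaves the emergency procedure as it is.
4. In section 6, report intervention-related events per patient descriptively beside the feasibility results, with an exact upper bound and the denominator stated.
5. Reconcile the toxicity collection times in 4.13 with the study calendar.

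Cost: two relatedness fields, one question at a contact that already takes place, and one descriptive table. The downside is a few more minor events to log. No visits are added and the sample size is unchanged.
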